7.4.2. Liver Biochemistry Assessments for Potential Hepatic Injury or Hepatic Decompensation

[figure not shown]
Liver biochemistry will be assessed to evaluate biochemical triggers that will prompt an immediate reevaluation of patients for potential hepatic injury or hepatic decompensation. These assessments will be performed at:

- Each protocol-specified visit (Table 1)
- Unscheduled visits as needed in the event of signs or symptoms of suspected hepatic injury or decompensation or if laboratory alerts have been triggered

It is important that the laboratory assessments be completed as required and that the central laboratory be used for assessments whenever possible. In the event that a patient cannot return to the clinic for a scheduled or unscheduled visit, or there is an event that triggers a need for an immediate assessment, the use of a local lab is permissible at the discretion of the Investigator. In these cases, the Investigator will obtain the laboratory results and the laboratory normal ranges.

The process for assessing criteria is presented in Figure 2, and the specific threshold(s) for each laboratory analyte to trigger mandatory repeat testing and, potentially, a complete patient evaluation (depending on the repeat result) are summarized in Table 3.

Figure 2: DILI Management Algorithm

DILI = drug-induced liver injury; IP = Investigational Product

NOTE Other laboratory criteria include: ALT, AST, total bilirubin, INR, and electrolytes (sodium).

Table 3: Liver Laboratory Criteria for Monitoring of Suspected Hepatic Injury or Potential Hepatic Decompensation and Criteria for Interruption or Discontinuation of Investigational Product

A. Laboratory Criteria for Monitoring Suspected Hepatic Injury		
Laboratory Parameter	Action Taken	Rechallenging Criteria
Total Bilirubin		If a patient interrupts IP, they may be rechallenged after a minimum of 30 days if fully resolved OR stable and approved by the Medical Monitor and Investigator.
Baseline \leq ULN and \geq 3x baseline	Interrupt IP	
Baseline $>$ ULN and \geq 2x Baseline	Interrupt IP	
ALT or AST		
$>$ 3x baseline (and $>$ ULN)	Interrupt IP	
\geq 2x baseline	Repeat Test in 2 to 3 days, interrupt IP if still elevated	
Electrolytes^a		
Sodium $<$ 130 mEq/L	Repeat Test in 2 to 3 days, interrupt IP if still below limit	
B. Laboratory Criteria for Monitoring Potential Hepatic Decompensation (Absence of Clinical Symptoms)		
Total Bilirubin	Closely monitor until normalization or stabilization.	The patient may be rechallenged after a minimum of 30 days if fully resolved OR stable and approved by the Medical Monitor and Investigator.
Baseline \leq ULN and 1.5 mg/dL increase from baseline	If values continue to increase relative to the baseline value, interrupt IP.	If laboratory values do not normalize, IP should not be restarted.
Baseline $>$ ULN and 1.0 mg/dL increase from baseline		
INR^b	Closely monitor until normalization or stabilization.	The patient may be rechallenged after a minimum of 30 days if fully resolved OR stable and approved by the Medical Monitor and Investigator.
$>$ 0.3 increase from baseline	If values continue to increase relative to the baseline value, interrupt IP.	If laboratory values do not normalize, IP should not be restarted.
\geq 2.0 unless due to vitamin K deficiency	Discontinue IP permanently	Continue to return for scheduled study visits for safety follow up. Monitor closely for clinical outcomes per protocol.
C. Laboratory Criteria for Monitoring Potential Hepatic Decompensation in the Presence of Clinical Symptoms		
Total bilirubin thresholds defined in Part B OR an INR increase from baseline of \geq 1.5 are observed in the presence of clinical symptoms of cholestatic hepatitis or hepatic encephalopathy ^c	Discontinue IP permanently	Continue to return for scheduled study visits for safety follow up. Monitor closely for clinical outcomes per protocol.

IP = investigational product

^a Sodium will be measured as an assessment of liver failure (hyponatremia).

^b Does not apply in patients on anti-coagulants.

^c Symptoms of cholestatic hepatitis includes dark urine and jaundice. Symptoms of hepatic encephalopathy may include lack of awareness, shortened attention span, lethargy, gross disorientation, or coma (unresponsive to verbal or noxious stimuli).

It should be noted that it is difficult to recognize every potential marker of hepatic or renal deterioration. There is no substitute for good medical judgment. Investigators will be reminded to be cautious and mindful in their evaluation of patients' symptoms, signs, and laboratory results. However, for example, a single abnormal laboratory analyte result may be artefactual; accordingly, Investigators will be allowed to implement an alternate follow-up procedure if considered appropriate based on their medical judgement, but only after documented agreement with the Sponsor's Medical Monitor.

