8.4. Dose Adjustment, Interruption, and Withdrawal from Investigational Product or Study

Investigational product may be temporarily decreased (eg, from 10 mg twice weekly to 5 mg twice weekly, or from 5 mg twice weekly to 5 mg once weekly) or temporarily or permanently stopped based on tolerability concerns. Investigational product may be resumed at the maintenance dose upon resolution of gastroenteritis or worsening renal function or dehydration if there is no evidence of liver injury. For rechallenge following all other dose interruptions (see Table 5), investigational product should be initiated at a lower dose and patients monitored more frequently with up-titration considered based on tolerability.

Adjustments, interruptions, discontinuation, and any rechallenge of investigational product should be implemented per the criteria outlined in Table 5. Patients that discontinue investigational product are expected to continue in the study (and follow the regular visit schedule, with the exception of PK sampling [trough PK may be required in the event of an AE consistent with hepatic injury or decompensation]) until the end of the study, but may withdraw consent at any time.

Table 5: Criteria for Dose Adjustment, Interruption, Discontinuation, and Rechallenge

DOSE ADJUSTMENT		
Criteria	Action Taken with IP	Adjustment
New Onset Severe Pruritus	Drug holiday or less frequent dosing	Return to original dose regimen if tolerated
DOSE INTERRUPTION		
Criteria	Action Taken with IP^a	Rechallenge^b
If liver biochemistries indicative of suspected hepatic injury are identified as exceeding upper threshold criteria and require immediate interruption (see Part A of Table 3) ^c	Interrupt immediately upon initial observation	Patient may be rechallenged after a minimum of 30 days if fully resolved OR stable and approved by the Medical Monitor and Investigator.
Other liver biochemistries indicative of suspected hepatic injury are outside upper threshold criteria upon repeat testing as defined in Part A of Table 3 ^d	Interrupt after confirmation by repeat testing	
Liver biochemistries indicative of potential hepatic decompensation in the absence of symptoms (see Part B of Table 3) ^e	Closely monitor until normalization or stabilization. If values continue to increase relative to the baseline value, interrupt	

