Clinical events indicative of hepatic decompensation (see Part B of Table 4)	Closely monitor until normalization or stabilization	The patient may be rechallenged after a minimum of 30 days if fully resolved OR stable and approved by the Medical Monitor and Investigator. IP should be re-initiated at a lower dose (or lower dose frequency) and titrated per Investigator discretion.

Gastroenteritis (established severe abdominal pain, vomiting, diarrhea for more than 4 days)	Interrupt	If no evidence of liver injury is detected, IP may be restarted at the same dose after resolution of intercurrent illness.
Evidence of worsening of renal function or dehydration	Interrupt	
DOSE DISCONTINUATION		
Criteria	Action Taken with IP	Rechallenge
If INR increases ≥ 2.0 in absence of clinical symptoms criteria (unless due to vitamin K deficiency) ^f	Discontinue / No Rechallenge	Discontinue IP permanently and continue to return for scheduled study visits for safety follow-up. Continue to return for scheduled study visits for safety follow-up. Monitor closely for clinical outcomes according to protocol assessments.
If total bilirubin thresholds (Part B of Table 3) are observed in the presence of clinical symptoms of cholestatic hepatitis or hepatic encephalopathy ^f		
Multi-Organ failure requiring hospitalization		
Liver transplantation		
Pregnancy		

Fully resolved = Return to baseline levels or return to within normal limits (WNL). IP = investigational product

^a If patient is unable to be evaluated promptly, study drug must be immediately interrupted.

^b Requires complete documentation of complete resolution or normal/baseline results based on laboratory parameters and symptoms.

^c Total bilirubin baseline \leq ULN and $\geq 3x$ baseline, baseline $>$ ULN and $\geq 2x$ baseline, ALT or AST $> 3x$ baseline (and $>$ ULN)

^d ALT or AST $\geq 2x$ baseline or electrolytes (sodium < 130 mEq/L).

^e Total bilirubin baseline \leq ULN and 1.5 mg/dL increase from baseline OR baseline $>$ ULN and 1.0 mg/dL increase from baseline; INR > 0.3 increase from baseline

^f If INR increases ≥ 2.0 in the absence of clinical symptoms or if or total bilirubin thresholds OR an INR increase from baseline of ≥ 1.5 are observed in the presence of clinical symptoms of cholestatic hepatitis or hepatic encephalopathy.

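### After a Table 3 Part B interruption, a bilirubin or INR that is stable above both baseline and the normal range may be restarted under one rule and is barred by two others

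*Protocol*

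**What the plan says.** Table 3 Part B (Section 7.4.2) covers rises in total bilirubin or INR without clinical symptoms. Once a threshold is crossed, the action is "Closely monitor until normalization or stabilization", and drug is interrupted if values go on rising from baseline.

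For both bilirubin and INR the rechallenge cell then holds two sentences. The first is "The patient may be rechallenged after a minimum of 30 days if fully resolved OR stable and approved by the Medical Monitor and Investigator". The second is "If laboratory values do not normalize, IP should not be restarted".

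Table 5 (Section 8.4) lists the Part B laboratory rise among its interruption criteria. Its rechallenge entry is "Patient may be rechallenged after a minimum of 30 days if fully resolved OR stable and approved by the Medical Monitor and Investigator", with no ban after it. Footnote b, attached to the heading of that rechallenge column, asks for documentation that the abnormality has completely resolved or that results are normal or at baseline. The legend below the table defines 'fully resolved' as a return to baseline or to within normal limits.

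The liver-failure entry of Table 4 Part B (Section 7.4.3) refers to Table 3 Part B and carries the permissive rule, with re-initiation at a lower dose or frequency.

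**The concern.** Both sentences in the Table 3 cell apply to the same patient at the same decision, and they give opposite answers when a value has settled without coming back to baseline or normal. Table 5 adds a second copy of the permission and a second, independent bar.

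The decision is whether to re-expose a Child-Pugh B or C patient after a laboratory sign of possible hepatic decompensation. Section 5.5 relies on rules-based laboratory monitoring for this risk. About 35 sites are planned. Two sites could handle identical patients in opposite ways and each cite the protocol, and a restart approved because the value is stable would breach the next sentence and footnote b.

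**Working it through.** The plan states no figure here that could be reproduced. The check is a comparison of the rules, followed by worked cases to show that the conflict can be reached.

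**Step 1: what 'stable' adds.** By the Table 5 legend, 'fully resolved' covers every value back at baseline or within normal limits. The word 'stable' therefore adds only values above both. The action column of Table 3 Part B also names normalization and stabilization as two different outcomes, so 'stable' cannot be read as another word for normalized.

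**Step 2: what each rule does with a value at day 30 or later, approval given.**

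| Value | Permission (Tables 3 and 5) | Ban (Table 3 Part B) | Footnote b (Table 5) |
|---|---|---|---|
| Within normal limits | restart allowed | no bar | met |
| Back at an abnormal baseline | restart allowed | unclear whether this counts as normalized | met |
| Stable above both | restart allowed | barred | not met |

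Only the last row is a clear contradiction.

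**Step 3: thresholds for bilirubin (mg/dL).** Part B limit: baseline + 1.5 if baseline is at or below the upper limit of normal (ULN), baseline + 1.0 if above. Part A limit: 3 × baseline, or 2 × baseline, respectively. The protocol gives no ULN; I assume 1.2 (range 1.0 to 1.3). The baselines and later values are also assumed.

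- *Baseline 2.4 (above ULN across the range).* Part B limit 2.4 + 1.0 = 3.4. Part A limit 2 × 2.4 = 4.8. Values of 3.5 and then 3.9 lead to a Part B interruption. If 3.9 holds for 30 days it is 3.9 − 2.4 = 1.5 above baseline and above ULN. The permission admits it; the ban and footnote b exclude it.
- *Baseline 1.0 (at or below ULN).* Part B limit 1.0 + 1.5 = 2.5. Part A limit 3 × 1.0 = 3.0. Values of 2.6 and then 2.8 lead to interruption. A plateau at 1.8 is above baseline and above any ULN in the range, so the rules split. A plateau at 1.1 is normal at ULN 1.2 and raises no conflict; at ULN 1.0 it would.

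**Step 4: INR.** The Part B threshold is a rise of more than 0.3. With an assumed baseline of 1.3, taken to be above normal, it is 1.3 + 0.3 = 1.6. Values of 1.7 and then 1.8 lead to interruption. A plateau at 1.8 is below the permanent stop at 2.0, and the rules split in the same way. A Part B INR interruption below that stop needs baseline + 0.3 < 2.0, so baseline < 1.7. That limit holds only where an INR of 2.0 or more is not due to vitamin K deficiency, because the permanent stop exempts that cause. The INR rules do not apply to patients on anticoagulants.

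**Step 5: can other text settle it?** Approval by the Medical Monitor and Investigator is a condition of the permission; the ban has no exception for approval. The paragraph after Table 3 says "Investigators will be allowed to implement an alternate follow-up procedure if considered appropriate based on their medical judgement". It requires documented agreement with the Medical Monitor, and its example is a single artefactual result. It does not say which restart rule governs.

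**The case against.** The strongest reply is that this is a wording slip inside a well-guarded clinical rule. Withholding drug satisfies every sentence. A restart needs at least 30 days off drug and the agreement of both Medical Monitor and Investigator. Section 8.4 adds that "investigational product should be initiated at a lower dose and patients monitored more frequently with up-titration considered based on tolerability". Patients with jaundice, dark urine or encephalopathy symptoms fall under Part C and stop permanently, which thins out the bilirubin cases. All of this stands. It limits the consequence without saying which sentence prevails.

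A second reply is that the permissive phrase recurs in Table 3 Parts A and B, Section 7.4.3, Table 4 and Table 5, and so looks deliberate. That is fair, and it means the sponsor may really want 'stable' to count. But then the ban and footnote b are wrong. Reading the ban as a limit on the permission fails too, because 'stable' would then have no effect.

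A reader might go further and infer that larger rises have a looser restart rule, because Part A says "If a patient interrupts IP, they may be rechallenged after a minimum of 30 days if fully resolved OR stable" with no ban after it. The documents do not support this. For a baseline b above ULN, b + 1.0 < 2b whenever b > 1.0, so with a ULN of at least 1.0 every bilirubin value at the Part A limit has also crossed the Part B limit. At or below ULN, b + 1.5 < 3b gives the same for b > 0.75. Nothing says that meeting Part A switches off the Part B sentence for a symptom-free patient. Footnote b also sits on the rechallenge column that serves the Part A rows.

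**Conclusion.** The contradiction is real and narrow. After an interruption for a symptom-free bilirubin or INR rise, a value stable above both baseline and the normal range may be restarted after 30 days with approval, and is also barred by the next sentence of the same cell and by Table 5 footnote b. It should be corrected, because it concerns re-dosing in a high-risk population and the protocol gives no order of precedence.

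Its size in patients cannot be worked out: the protocol gives no rate of Part B interruptions or of plateaus above baseline. The worked values rest on an assumed ULN and assumed baselines; the conflict between the two Table 3 sentences does not. The extracted Table 5 is broken, and I read its rechallenge cell as shared by the three laboratory rows. The Table 3 conflict does not depend on that reading either.

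A reader might infer that the text directs unsafe re-exposure. It does not: it permits and forbids the same restart, and the cautious choice is always compliant.

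**What to change.** In Table 3 Part B, for both bilirubin and INR, replace the two sentences with one rule: restart no sooner than 30 days after interruption, only when the value is back at baseline or within normal limits, and only with agreement of the Medical Monitor and Investigator; in every other case the drug stays off. This removes 'stable' and replaces 'normalize' with the protocol's own definition of full resolution, which also settles the abnormal-baseline row above. Give the Part B row of Table 5 its own rechallenge entry with the same text, and make the Table 4 liver-failure entry that cites Table 3 Part B consistent with it.

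If the sponsor intends 'stable' to count, delete the ban, amend footnote b and define 'stable': number of tests, interval between them, and the highest acceptable value above baseline.

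The cost is wording in three tables through a protocol amendment, with no new visit or procedure. It does need clinical decisions: whether 'stable' counts for Part B and, if it does not, whether the other Table 4 Part B events (such as variceal bleeding or Grade 2 or higher encephalopathy) should still be restartable when stable.

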7.4. Monitoring and Management of Potential Hepatic Injury and/or Disease Progression

Given the chronic nature of PBC, it is important to monitor for potential hepatic injury, disease progression and/or hepatic decompensation. Child-Pugh and MELD scores will be reviewed at each visit where labs are drawn (Table 1). In addition, adverse events, signs and symptoms of potential hepatic injury or decompensation, and laboratory values will also be reviewed at regular intervals as described in Section 7.1.2. Based on biochemical and clinical assessments, the investigational product may be interrupted or discontinued per criteria discussed in

Section 7.4.2 and [Section 7.4.3](#), and close monitoring procedures will be implemented (refer to [Section 7.6](#)).

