
 • Liver failure defined as worsening synthetic function that is persistently worse relative to baseline and/or progressive over time (see Table 3, Part B)^a • Variceal bleeding or recurrent variceal bleeding^b documented by endoscopy or accompanied by anemia or melena with a hemoglobin drop of ≥ 2 g/dL • Ascites^c including: 
 ○ Worsening – requires increase in drug therapy or surgical intervention (paracentesis or shunt procedure) ○ Refractory ascites – unresponsive to medication; patient not candidate for transjugular intrahepatic portosystemic shunt (TIPS) or shunt; requires large volume paracentesis ○ Hyponatremia (≤ 125 mEq/L) secondary to ascites • Spontaneous Bacterial Peritonitis • Hepatic Encephalopathy, Grade ≥ 2 • Any liver-related event requiring hospitalization and treatment (except multi-organ failure) • Hepatorenal syndrome Type 1 or Type 2 and acute kidney injury, hepatopulmonary syndrome, or portopulmonary syndrome 	
Closely monitor until normalization or stabilization.
 
The patient may be rechallenged after a minimum of 30 days if fully resolved OR stable and approved by the Medical Monitor and Investigator
 
IP should be re-initiated at a lower dose (or lower dose frequency) and titrated per Investigator discretion.

^a Patients experiencing INR ≥ 2.0 unless due to vitamin K deficiency should be discontinued from IP permanently without rechallenge and should return for scheduled study visits for safety follow up.

^b Endoscopic confirmation of gastric or duodenal varices without evidence of bleeding should be closely monitored; investigational product may be interrupted at Investigator discretion

^c New onset ascites requiring treatment should be closely monitored; investigational product may be interrupted at Investigator discretion

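### The INR rule for permanent discontinuation is a level in Tables 3 and 4 but is worded as an increase in Table 5, and it makes no provision for patients who enter at or above it

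*Protocol*

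**What the plan says.** The rule for permanently stopping investigational product on INR appears in three places in the Protocol.

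- **Section 7.4.2, Table 3 Part B (no clinical symptoms):** permanent discontinuation at INR ≥"2.0 unless due to vitamin K deficiency". Footnote b, attached to the INR heading, adds: "Does not apply in patients on anti-coagulants". The row above, for a rise of more than 0.3 from baseline, calls for monitoring and for interruption if the value keeps rising.
- **Section 7.4.3, Table 4 footnote a:** patients with INR ≥2.0, with the same vitamin K exception, "should be discontinued from IP permanently without rechallenge". The footnote hangs on the liver-failure row, which describes worsening synthetic function and refers back to Table 3 Part B.
- **Section 8.4, Table 5:** the discontinuation row begins "If INR increases" and continues with ≥2.0 and the vitamin K exception. Footnote f repeats the increase wording and goes on "in the absence of clinical symptoms or if or total bilirubin thresholds OR an INR increase from baseline of" ≥1.5 for patients with symptoms.

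Table 3 Part C, for symptomatic patients, reads "Total bilirubin thresholds defined in Part B OR an INR increase from baseline of" ≥1.5.

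Two sections direct sites to these tables. Section 7.4 says "the investigational product may be interrupted or discontinued per criteria discussed in" Sections 7.4.2 and 7.4.3, that is, Tables 3 and 4. Section 8.4 says adjustments, interruptions, discontinuations and rechallenge "should be implemented per the criteria outlined in Table 5". The text does not say which governs if they differ.

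**The concern.** Sites apply this rule to individual patients. It is mandatory, allows no rechallenge, and concerns hepatic safety in a population the Protocol itself describes as at elevated risk of decompensation. Its threshold should have one meaning. As written, a site working from Table 3 and a site working from Table 5 could act differently on the same INR.

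Two gaps follow from the same text. Table 5 does not carry the anticoagulant exemption, although Section 9.2.1 foresees patients on warfarin adjusted to a target INR. And if the rule is a level, Table 3's row has no baseline condition, while entry is limited only by Child-Pugh score and MELD. A patient with a stable high INR could be randomized and already meet a permanent stop. That patient would probably contribute no usable on-treatment serial PK profile: the first is at Week 12, and Section 8.4 drops PK sampling after discontinuation.

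**Working it through.** The Protocol states no figure to reproduce. The check compares the wordings and works out where each reading acts.

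**1. Where the stop falls.** Level reading: INR 2.0. Rise reading of Table 5: baseline + 2.0. Part C's INR limb, with symptoms: baseline + 1.5.

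| Baseline INR | Level | Rise | Part C INR limb |
|---|---|---|---|
| 1.2 | 2.0 | 3.2 | 2.7 |
| 1.5 | 2.0 | 3.5 | 3.0 |
| 1.8 | 2.0 | 3.8 | 3.3 |
| 2.1 | already met | 4.1 | 3.6 |

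The gap between the readings is (baseline + 2.0) − 2.0, which is the patient's own baseline INR.

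**2. One patient, two actions.** Take an asymptomatic patient going from 1.2 to 2.5. Under Table 3 the level is exceeded and product stops for good. Under Table 5 read as a rise, the change is 2.5 − 1.2 = 1.3, below 2.0 but above 0.3. The patient is monitored, interrupted if the INR keeps rising, and may be rechallenged after at least 30 days if resolved or stable and approved by the Medical Monitor and Investigator. Table 3 adds that product is not restarted if values do not normalize.

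**3. Level rule and the monitoring row.** 1.7 + 0.3 = 2.0. From a baseline of 1.7, where Table 12's two-point INR band begins, the level stop is reached before the >0.3 row is exceeded.

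**4. Entry with INR ≥2.0.** Sections 8.2 and 8.3 admit Child-Pugh 7 to 12 and MELD 6 to 24 and give no INR limit. Table 12 scores INR 1.7 to 2.3 as 2 points and above 2.3 as 3. Two examples:

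- Bilirubin 2.5 mg/dL (2) + albumin 3.6 g/dL (1) + INR 2.1 (2) + no ascites (1) + no encephalopathy (1) = 7, CP-B.
- Bilirubin 3.5 (3) + albumin 3.0 (2) + INR 2.1 (2) + mild ascites (2) + no encephalopathy (1) = 10, CP-C.

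MELD combines bilirubin, creatinine and INR, so capping the total does not by itself cap INR. The Protocol prints no formula. As an assumption only, take 3.78 ln(bilirubin) + 11.2 ln(INR) + 9.57 ln(creatinine) + 6.43. At INR 2.0, with bilirubin 1 to 8 mg/dL and creatinine 1.0 to 1.3 mg/dL, this runs from 14.2 to 24.6, above 24 only at the upper extreme.

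**5. PK sizing (Section 15.2).** The PK requirement is 20 on OCA with 15% discontinuation: 20 × 0.85 = 17. With 50 randomized 1:1, 25 × 0.85 = 21.25, a margin of about four patients.

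**The case against.** The strongest reply is that Table 5 merely lost a word and means that INR increases to 2.0. Wherever the tables clearly mean a change they say so relative to baseline: the >0.3 row, Part C, and the second half of footnote f. The ≥2.0 item never carries that qualifier, and much of Table 5 restates Tables 3 and 4. This stands as evidence of intent. It does not remove the ambiguity, because footnote f puts the increase wording beside an explicit rise of 1.5, and a site could reasonably read 2.0 without symptoms and 1.5 with symptoms as a matched pair.

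A reader might infer more than the documents support:

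- **That Table 4 footnote a forces a stop in a patient on warfarin, or in one with a stable high INR.** The footnote qualifies a row about worsening function and refers to Table 3 Part B, where the anticoagulant exemption sits. It fails to repeat the exemption; it does not clearly override it. The stable entrant is caught by Table 3's row, not cleanly by Table 4.
- **That the level stop always comes before Part C's INR limb.** Not in vitamin K deficiency, which the ≥2.0 row exempts and Part C does not.
- **That sites are bound to diverge.** Section 7.6 requires such cases to be discussed with the Medical Monitor, and Section 7.4.2 allows alternate follow-up by documented agreement. Both reduce divergence, but neither says which threshold governs.

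Figure 2, which presents the process for assessing the criteria, is not reproduced in the available text, so the absence of a precedence rule is established for the text only.

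**Conclusion.** The point holds as an inconsistency in a mandatory safety rule. The same threshold is a level in two tables and is worded as an increase in the third, and the two readings differ by the patient's baseline INR. The level is probably what is meant; the documents do not support a claim that the sponsor intended a rise of 2.0. Table 5 also drops an exemption that Table 3 grants.

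The entry mismatch depends on the level reading and on Table 3's row, and applies only to patients who are neither anticoagulated nor vitamin K deficient. The Child-Pugh examples rest on Table 12; fitting the MELD window rests on the assumed formula. The number entering at INR ≥2.0 is not given and cannot be estimated from the Protocol. Nothing here shows that the PK objective is undersized. This should be corrected, but it does not put the trial's main analyses in doubt.

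**What to change.** Make three wording changes:

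1. In Table 5 and footnote f, replace the increase wording with Table 3's rule: INR ≥2.0, unless due to vitamin K deficiency, and not applicable to patients on anticoagulants.
2. Repeat the anticoagulant exemption in Table 4 footnote a.
3. In all three places, limit the level rule to patients with baseline INR below 2.0, and state a baseline-relative limit, set by the clinical team, for those entering at 2.0 or above.

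An INR exclusion in Section 8.3 would also close the entry gap, but it would narrow the population the study exists to characterize, so the baseline-relative limit is preferable.

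The cost is a protocol amendment to safety sections that were revised at FDA request, so regulatory agreement would be needed. INR is already measured at Screening, Day 1 and each laboratory visit, so no new assessment is required, and Section 15.2 does not change.

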7.4.3. Clinical Criteria for Monitoring for Potential Hepatic Decompensation

Patients will be monitored for potential hepatic decompensation events throughout the study. Clinical criteria for monitoring these events and the interruption/discontinuation of investigational product is summarized in [Table 4](#).

Investigational product should be discontinued permanently if the patient received a liver transplant or experiences multi-organ failure as defined in Table 4, Part A. Patients should continue to return for scheduled study visits for safety follow-up.

Patients who experience other potential hepatic decompensation events defined in Table 4, Part B should be closely monitored until normalization or stabilization. Patients may be rechallenged after a minimum of 30 days if fully resolved OR stable and approved by the Medical Monitor and Investigator.

Table 4: Clinical Criteria for Monitoring Potential Hepatic Decompensation Events and Interruption / Discontinuation of Investigational Product

A. Hepatic Decompensation Events Requiring Mandatory Discontinuation of Investigational Product	
Decompensation Event	Action Taken / Rechallenging Criteria
Liver Transplant Multi-organ failure requiring hospitalization	Discontinue IP permanently and follow patients until normalization/stabilization. Continue to return for scheduled study visits for safety follow up.
B. Hepatic Decompensation Events Requiring Interruption of Investigational Product	

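### Hepatic encephalopathy of grade 2 or higher, or a liver-related hospitalization with jaundice or dark urine, combined with a Table 3 Part B bilirubin rise, is both a permanent stop and an event open to rechallenge, and no precedence is stated

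*Protocol*

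**What the plan says.** **Permanent stop.** Table 3 Part C (Section 7.4.2) applies when "Total bilirubin thresholds defined in Part B OR an INR increase from baseline of" 1.5 or more "are observed in the presence of clinical symptoms of cholestatic hepatitis or hepatic encephalopathy". The action is "Discontinue IP permanently". The Part B thresholds it borrows are, for a baseline at or below, "ULN and 1.5 mg/dL increase from baseline" and, for a baseline above, "ULN and 1.0 mg/dL increase from baseline". Footnote c counts dark urine and jaundice as cholestatic symptoms. The discontinuation block of Table 5 (Section 8.4) repeats the bilirubin rule and rules out rechallenge; its footnote f adds the INR rise of at least 1.5.

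**Rechallenge possible.** Table 4 Part B (Section 7.4.3) is headed as a list of events requiring interruption. It includes encephalopathy of grade 2 or higher, and liver-related events leading to hospitalization and treatment, excepting only multi-organ failure. For these: "The patient may be rechallenged after a minimum of 30 days if fully resolved OR stable and approved by the Medical Monitor and Investigator". Restart is at a lower dose or lower frequency. The Section 7.4.3 text agrees: "Patients who experience other potential hepatic decompensation events defined in Table 4, Part B should be closely monitored until normalization or stabilization", followed by the same 30-day provision. The interruption block of Table 5 repeats it, referring to Table 4 Part B.

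**The concern.** The two sets of criteria are not mutually exclusive. Encephalopathy of grade 2 or higher carries no bilirubin or INR condition in Table 4, and the Part C trigger has no upper limit on clinical severity. One decompensation can therefore meet both. One set then forbids any further dosing and the other permits it subject to approval.

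Two things are at stake. The first is patient safety: whether a patient is re-exposed after a serious hepatic event should follow from a stated rule, not from the row that happens to be applied. The second is interpretability: discontinuations are listed among the primary safety assessments in Section 11 (Table 7), and a permanently stopped patient leaves the regular PK sampling schedule under Section 8.4.

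**Working it through.** The protocol states no figure to reproduce here, so the check is a test of overlap between rules.

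**Step 1. Apply each rule to the same patient.**

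| Patient | Table 3 Part C and Table 5 discontinuation block | Table 4 Part B, Section 7.4.3 and Table 5 interruption block |
|---|---|---|
| Grade 2 or higher encephalopathy; bilirubin up 1.0 mg/dL (baseline above ULN) or 1.5 mg/dL (baseline at or below ULN) | Permanent stop, no rechallenge | Rechallenge possible after at least 30 days, on conditions |
| Treated liver-related hospitalization with jaundice or dark urine, same bilirubin rise, no multi-organ failure | Permanent stop, no rechallenge | Rechallenge possible after at least 30 days, on conditions |
| Grade 2 or higher encephalopathy, no Part B bilirubin rise and no INR trigger | Not triggered | Rechallenge possible, on conditions |
| Milder encephalopathy symptoms with a Part B bilirubin rise, no Table 4 event | Permanent stop | Not triggered |

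Only the first two rows conflict.

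**Step 2. Look for an exception.** Table 4 Part A takes out liver transplant and multi-organ failure. The hospitalization item excepts multi-organ failure. Footnote a imports a permanent stop for INR of 2.0 or more unless due to vitamin K deficiency. Footnotes b and c deal with varices without bleeding and new ascites. None refers to Table 3 Part C.

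**Step 3. Look for a precedence rule.** Section 7.4.1 sends the patient through Section 7.4.2, then 7.4.3, then 8.4. Section 8.4 makes Table 5 the governing list, and Table 5 contains both rules. No order is given. Figure 2, which Section 7.4.2 cites for the assessment process, is not shown, so it cannot be checked.

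**Step 4. The INR route.** Baseline INR + 1.5 is at least 2.0 whenever baseline INR is at least 0.5, so nearly every Part C INR rise also meets the level of 2.0 in Table 3 Part B and Table 4 footnote a. What remains is mainly an INR rise attributed to vitamin K deficiency, which the 2.0 rule exempts and Part C does not. Bilirubin is the main route to conflict.

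**Step 5. Size for one patient.** For an event at Week t, the most time left on drug to Week 48 after rechallenge is 48 − t − 30/7 weeks; after a permanent stop it is 0. The event week is an assumption:
- t = 12: 36 − 4.3 = 31.7 weeks
- t = 20: 28 − 4.3 = 23.7 weeks
- t = 36: 12 − 4.3 = 7.7 weeks

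These are upper bounds, because restart also needs resolution or stability and approval. In the count of permanent discontinuations, one such patient is 1 or 0. With about 50 randomised 1:1, an arm has 50/2 = 25, so one patient is 1/25 = 4 percentage points.

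**The case against.** The best reply is that the rules can be applied together. Part C is mandatory and narrower (a laboratory value plus symptoms), while Table 4 only permits rechallenge. Stopping permanently breaches nothing in Table 4; rechallenging breaches Part C. This is a plausible reading, but the protocol does not state it. Table 4 also carries across one permanent stop from Table 3 (INR of 2.0 or more) and not the other, which invites the opposite reading.

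The safeguards are real. Rechallenge needs agreement from both the Medical Monitor and the Investigator, is at a lower dose or frequency, and under Table 5 footnote b needs documented resolution or normal or baseline results. The Medical Monitor is contacted about every such event, so sites do not decide alone. This limits variation between sites, but the approver faces the same two rules. The clause in Section 7.4.2 allowing an alternate follow-up by documented agreement is case by case and does not choose between them.

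A reader might infer more than the text supports:
- **That the PK sample size is at risk.** The 20 OCA patients in Section 15.2 already allow for 15% discontinuation: 20 − 0.15 × 20 = 17 completers. With about 25 on OCA, 25 − 17 = 8 losses would be needed before falling below 17. The PK Population requires adequate profiles, not Week 48 completion; a patient stopped at Week 20 could already have the Week 12 and Week 18 serial profiles.
- **That the comparison between arms is biased.** Sponsor, sites and patients are blinded (Section 9.4.2), so inconsistent application gives no evident reason for a systematic difference, and safety is descriptive.
- **That the thresholds are misplaced relative to severity.** Where a clinical threshold sits is a clinical judgement, not a contradiction.
- **That the liver-failure item in Table 4 is a further clear overlap.** It points to Table 3 Part B, which is headed as applying without clinical symptoms, and so tends to separate the two cases.

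**Conclusion.** The point stands as an internal contradiction in a patient-safety instruction, confined to patients who meet a Table 4 Part B event and the Table 3 Part C combination together. For them the protocol both forbids and conditionally permits further dosing, and Table 5 repeats both rules. The consequence is per patient: re-exposure or none after a decompensation, and a shift of about 4 percentage points per patient in one arm's permanent-discontinuation count.

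How often this would occur cannot be stated, because the protocol gives no frequency for the combination. The conclusion rests on the visible text and assumes that Figure 2 does not settle the order. It takes no position on which rule is clinically right.

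**What to change.** Reconcile Table 3 Part C, Table 4 Part B, Section 7.4.3 and the interruption and discontinuation blocks of Table 5. The sponsor's medical team should decide which rule governs when an event meets both and say so in each place, for example by a footnote to Table 4 Part B in the manner of footnote a and a matching line in Table 5. Check Figure 2 against the result. Record on the eCRF which criterion interrupted or ended dosing, so that discontinuations can be tabulated by cause.

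The cost is a footnote and a table line in the next amendment, plus one eCRF item. No extra patients, visits or samples are needed.
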